9.2 Trial subjects

9.2.1 *Analysis samples*

For presentation of data and reporting of the statistical analyses, the following analysis samples will be used, depending on the context:

- Safety analysis set (SAS): All randomized subjects who received at least one dose of trial medication.
- Full analysis set (FAS): All randomized subjects who received at least one dose of trial medication.
- Per protocol (PP) set: All subjects of the FAS for whom no relevant protocol deviations were documented. This sample will primarily be used for sensitivity analysis.

The analysis of the primary endpoint and secondary endpoints will be based on the FAS. A secondary analysis of the primary endpoint will be based on the PP set. All safety analyses will be based upon the SAS.

The decision regarding whether a protocol deviation is relevant or not for the exclusion of subjects from the PP set will be made case-by-case in a data review meeting prior to treatment unmasking and database lock (see Section [9.2.3](#)).

9.2.2 *Disposition of subjects*

Subject disposition will be tabulated including the number of screened subjects, screening failures, subjects exposed to trial product, subjects completing the trial and subjects in each analysis set.

Subjects withdrawn from the trial will be listed including the primary reason for withdrawal.

9.2.3 *Protocol deviations*

Before data are released for statistical analysis, a treatment-masked review of all data will take place to identify protocol deviations that may potentially affect the results. This review will be performed without revealing to which trial product the subjects were assigned. The masking of the trial products will be maintained for everyone involved in allocating subjects to the analysis sets until data are released for statistical analysis.

Furthermore, spurious outliers will be evaluated. In addition, protocol deviations that may potentially affect the results will be identified and it will be evaluated if subjects and/or data should be excluded from the analysis. Protocol deviations will be classified as minor or major in a consistent way. Major deviations from the protocol may lead to the exclusion of a subject from the PP set.

Major protocol deviations may include deviations related to trial inclusion or exclusion criteria, conduct of the trial, subject management or subject assessment. Unless explicitly decided otherwise during the masked data review, the following will be considered major protocol deviations:

- Violation of one or more major inclusion/exclusion criteria
- Interruption of administration of trial product
- Significant deviation from time windows
- Incorrect treatment allocation
- Missing primary endpoint.

The violation of several major inclusion/exclusion criteria or the complete absence of efficacy data might lead to exclusion of the subject from FAS. In that case, the decision should be taken at the masked data review meeting, and the exclusion from efficacy analysis justified in the signed notes of the meeting.

Obviously erroneous data points may be excluded from the analyses or re-analyzed (in case of e.g. serum concentrations). The decision to re-analyze or exclude data points from the statistical analysis is the joint responsibility of the sponsor and the trial statistician.

The subjects or observations to be excluded and the reason for their exclusion will be documented and signed by those responsible prior to database release. The documentation will be stored together with the remaining trial documentation. The subjects and observations excluded from analysis sets, and the corresponding reasons, will be described in the clinical trial report.

9.3 General considerations

All data obtained in this trial and documented in the eCRFs will be listed and summarized with statistics or frequency tables as appropriate. In case of termination of the trial, all data collected up to that timepoint will be included in the analysis.

Raw data listings and summary tables will be generated using the software SAS[®] version 9.4 or higher.

Continuous variables will be summarized using means, standard deviations, medians, coefficients of variation, and minimum and maximum values.

Other summaries (e.g. quartiles, 95% confidence intervals [CIs]) may be used as appropriate. Categorical efficacy and safety variables will be summarized by counts and by percentage of subjects in corresponding categories.

9.4 Demographics and baseline characteristics

Baseline and demographic data will be summarized using descriptive statistics. Baseline ADA-positive subjects will be calculated as a percentage of the total number of subjects whose baseline samples were tested for ADA.

All other data obtained in this trial and documented in the eCRF will be listed.

9.5 Efficacy Analyses

For the confirmatory analyses, the primary and key secondary endpoints for the dasiglucagon 0.6 mg and placebo treated subjects will be compared. A hierarchical procedure will be applied for the control of multiplicity. The primary and secondary endpoints will be evaluated on the full analysis set. In the primary analysis, those subjects

who require rescue IV glucose will be censored at the time to plasma glucose recovery. In a sensitivity analysis, the time to plasma glucose recovery will be analyzed without censoring the subjects who received rescue IV glucose.

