In the primary analysis, recovery cannot be achieved in those subjects where IV glucose treatment is administered. Those subjects who receive IV glucose will be censored (i.e. set to 'not recovered') at 45 minutes after dosing.

In sensitivity analyses, the time to plasma glucose recovery will be analyzed 1) without censoring for those subjects who require rescue IV glucose before 45 minutes and 2) with censoring at the time of administration of rescue IV glucose before 45 minutes.

The primary endpoint will additionally be analyzed using a Cox proportional hazards (CPH) time to event statistical model, if the hazards by treatment group can be assumed proportional using a graphical comparison of log-minus-log survival curves and no more than two-thirds of the recovery times are censored in each treatment group. The CPH model will be used for inferences, with treatment group and injection site modeled as categorical effects, and baseline plasma glucose modeled as a continuous covariate. The treatment group rate ratios, active versus placebo, will be estimated together with the 95% confidence intervals, and pairwise treatment group inferences (dasiglucagon vs placebo, GlucaGen vs placebo) will be evaluated using two-sided likelihood ratio tests.

The key secondary incidence variables (plasma glucose recovery within 30 minutes, within 20 minutes, within 15 minutes, within 10 minutes, in hierarchical order for inference) will be analyzed using descriptive statistics (frequency and percentage) by treatment group. Inferential treatment group comparisons will be assessed via pairwise tests of independent binomial proportions (dasiglucagon versus placebo, GlucaGen versus placebo) using Fisher's exact test for each pairwise comparison.

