9.5.2.1 Primary analysis

The primary endpoint will be summarized using Kaplan-Meier (KM) estimates stratified by treatment group and injection site. The treatment group difference between dasiglucagon and placebo will be evaluated inferentially using a pairwise two-sided log-rank test.

In the primary analysis, recovery cannot be achieved in those subjects where IV glucose treatment is administered. Those subjects who receive IV glucose will be censored (i.e. set to ‘not recovered’) at 45 minutes after dosing.

In sensitivity analyses, the time to plasma glucose recovery will be analyzed 1) without censoring for those subjects who require rescue IV glucose before 45 minutes and 2) with censoring at the time of administration of rescue IV glucose before 45 minutes.

The primary endpoint will additionally be analyzed using a Cox proportional hazards (CPH) time to event statistical model, if the hazards by treatment group can be assumed proportional using a graphical comparison of log-minus-log survival curves and no more than two-thirds of the recovery times are censored in each treatment group. The CPH model will be used for inferences, with treatment group and injection site modeled as categorical effects, and baseline plasma glucose modeled as a continuous covariate. The treatment group rate ratios, active versus placebo, will be estimated together with the 95% confidence intervals, and pairwise treatment group inferences (dasiglucagon vs placebo, GlucaGen vs placebo) will be evaluated using two-sided likelihood ratio tests.

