9.9 Subject withdrawals and missing data

Failure is defined for the primary time-to-recovery endpoint as censored with time to recovery set to the maximum follow-up time, here 45 minutes. Individuals will be set to 'failure' in case of receiving rescue IV glucose, discontinuation due to treatment or discontinuation in connection with the induced hypoglycemia state. Only if an intermediate assessment is missing independent of rescue treatment, study treatment or an adverse event including hypoglycemia, interpolation can be applied to impute a missing value.

The same construct of imputation applies for the analysis of the plasma glucose AUC0-30min.

In the case of subject withdrawal, no imputation of values for PK or PD measurements will be done. Analyses will be done on valid cases only, i.e., no imputation techniques such as last observation carried forward will be applied.

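### Section 9.5 censors rescued subjects at glucose recovery while Section 9.5.2.1, the synopsis and Section 9.9 censor them at 45 minutes; 9.5 is the outlier and should be aligned before unmasking

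*Protocol*

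**What the plan says.** Four places in the current protocol version describe how rescued subjects enter the primary analysis.

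- Section 9.5, the introduction to the efficacy analyses: subjects "who require rescue IV glucose will be censored at the time to plasma glucose recovery". It then gives a single sensitivity analysis: "In a sensitivity analysis, the time to plasma glucose recovery will be analyzed without censoring the subjects who received rescue IV glucose".
- Section 9.5.2.1, Primary analysis: "recovery cannot be achieved in those subjects where IV glucose treatment is administered", followed by "Those subjects who receive IV glucose will be censored (i.e. set to ‘not recovered’) at 45 minutes after dosing". It lists two sensitivity analyses, one without censoring for rescue and one with censoring at the moment rescue is given.
- Synopsis, statistical methods: the same rule as 9.5.2.1, opening with "In the primary analysis, recovery cannot be achieved in those subjects where IV glucose treatment is administered", and the same two sensitivity analyses.
- Section 9.9, missing data: "Failure is defined for the primary time-to-recovery endpoint as censored with time to recovery set to the maximum follow-up time, here 45 minutes", with rescue named as a trigger: "Individuals will be set to 'failure' in case of receiving rescue IV glucose".

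The confirmatory comparison of dasiglucagon with placebo is "evaluated inferentially using a pairwise two-sided log-rank test". Section 9.5.1 places it first in the hierarchy, ahead of eight key secondary tests.

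**The concern.** Both rules are stated for the primary analysis, and the protocol gives no order of precedence. Neither lets a rescued subject count as a recovery. They differ in how long that subject stays in the risk set: under 9.5 until glucose has risen with the help of IV glucose, under the other three places until 45 minutes. The risk sets enter every Kaplan-Meier step and every term of the log-rank statistic, so the curves, medians and p-value depend on which sentence is followed. The test affected is the one on which the trial's claim and all key secondary claims depend.

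**Working it through.** **1. The stated power.** Inputs from Section 9.1: 78 and 39 subjects, exponential medians of 10 and 20 minutes, 45 minutes of follow-up, two-sided 5%.

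Expected recoveries by 45 minutes: 78 × (1 − exp(−45 ln2/10)) + 39 × (1 − exp(−45 ln2/20)) = 78 × 0.956 + 39 × 0.790 = 74.6 + 30.8 = 105.4.

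Schoenfeld power with hazard ratio 2 and allocation 2/3 : 1/3: Φ(√(105.4 × 2/3 × 1/3) × ln2 − 1.96) = Φ(3.35 − 1.96) = 91.8%.

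A log-rank simulation without rescue gives 90.4%. The stated 90% reproduces. It assumes no rescue, so it does not depend on the choice of rule.

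**2. Why the rules differ.** Suppose n subjects in an arm are at risk under the 45-minute rule and r of them have been rescued and already lifted by IV glucose. At the next recovery in that arm the Kaplan-Meier factor is 1 − 1/n under the 45-minute rule and 1 − 1/(n − r) under 9.5. In the log-rank test the dasiglucagon share of the risk set is n1/(n1 + n0) against (n1 − r1)/(n1 − r1 + n0 − r0). If rescue is mainly on placebo, 9.5 raises the number of recoveries expected on dasiglucagon and so lowers Z. With no rescue the two rules coincide.

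**3. Effect on the test.** Both rules were applied to the same simulated trials, 1,500 per scenario, with medians of 10 and 20 minutes. All rescue inputs are assumptions. Each subject carries a rescue flag with the probability shown. A flagged subject is rescued at a time uniform on 8-30 minutes if not yet recovered, and glucose recovers 2-10 minutes later.

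| Flag, dasiglucagon / placebo | Mean placebo subjects rescued (of 39) | Rejects, 9.5 rule | Rejects, 45-minute rule | Decisions differ |
|---|---|---|---|---|
| 0 / 0 | 0 | 90.4% | 90.4% | 0% |
| 0 / 20% | 4.1 | 91.9% | 95.8% | 3.9% |
| 0 / 40% | 8.3 | 91.2% | 98.0% | 6.8% |
| 5% / 40% | 8.3 | 91.2% | 96.2% | 5.0% |
| 20% / 20% | 4.1 | 87.8% | 83.7% | 5.8% |

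In the 0 / 40% row the mean Z is 3.29 under 9.5 and 3.94 under the 45-minute rule.

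**4. Effect on the placebo curve.** A separate simulation took 39 placebo subjects on the planned sampling times, where the last sample before 45 minutes is at 40. It assumed rescue at 8-20 minutes and a 20 mg/dL rise 5-15 minutes after rescue. The last column is the recovery seen by 40 minutes if nobody were rescued, 1 − 2^(−40/median).

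| No-rescue median, share rescued | Recovered, 45-minute rule | Recovered, 9.5 rule | No rescue |
|---|---|---|---|
| 20 min, 20% | 65.2% | 71.3% | 75% |
| 30 min, 38% | 46.2% | 53.6% | 60% |
| 40 min, 43% | 37.4% | 44.0% | 50% |

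Across all scenarios run, the 9.5 rule gave values 3-8 percentage points higher. In the second row the placebo median is not reached under the 45-minute rule and is 40 minutes under 9.5.

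**The case against.** The strongest reply is that nobody would be misled. Section 9.5 is an overview paragraph. The section that carries the primary analysis, the synopsis and the missing-data section all give the 45-minute rule. The earlier protocol versions in the same file show where the sentence came from: there 9.5 and 9.5.2.1 agreed on censoring at recovery, and 9.5 was not updated. This stands as to intent. It does not remove the conflict, because 9.5 speaks of the primary analysis in the present version and its list of sensitivity analyses also differs.

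Three stronger readings are tempting and are not supported.

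- A reader might infer that the confirmatory test is undefined, or that the rule could be picked after seeing results. The intended rule can be inferred from three places, and Section 9 requires the SAP to be final before database lock and unmasking.
- A reader might infer that the 9.5 rule favours dasiglucagon. When rescue falls mainly on placebo it is the conservative rule. It rejects more often only in the scenario with equal flags. The protocol's phase 2 summary (Section 2.1.3.1) makes that scenario less likely, since all subjects rose by at least 20 mg/dL within 30 minutes.
- A reader might infer from step 4 that 9.5 overstates placebo recovery through informative censoring. It does so only relative to counting rescue as failure. Both rules fall below the no-rescue values, and 9.5 is the nearer. That simulation does not tie rescue to falling glucose, so it shows two different target quantities and no demonstrated bias.

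**Conclusion.** The contradiction is real and lies in the primary analysis. Section 9.5 is wrong as written, measured against 9.5.2.1, 9.9 and the synopsis, and its list of sensitivity analyses is incomplete. Under assumed rescue flags of 0-40% per arm, rejection rates differ between the rules by about 4 to 7 percentage points wherever rescue occurs, in either direction, and the two rules reach different decisions in about 4-7% of trials. These sizes depend wholly on rescue rates and timings that the protocol does not give. The sample size and the stated 90% power are unaffected. A SAP may already apply the 45-minute rule, but that would leave the protocol sentence contradicting it.

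**What to change.** Before unmasking, delete the last two sentences of Section 9.5 and put a cross-reference to 9.5.2.1 and 9.9 in their place. Rescued subjects are then failures censored at 45 minutes throughout, and the sensitivity analyses are the two in 9.5.2.1. This costs one paragraph of wording and has no operational consequence.

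The replacement should not limit the rule to rescue given before recovery as though that were existing text, because 9.5.2.1, 9.9 and the synopsis contain no such limit. It matters for a subject who enters at 46 mg/dL, reaches 66 mg/dL (a rise of 20), and is then rescued at 45 minutes because glucose is below 70 mg/dL, as Section 8.2.3.1 provides. Read literally, 9.5.2.1 and 9.9 make that subject a failure; a rule limited to rescue before recovery would make the same subject a recovery. The statistical classification should be reconciled explicitly in 9.5.2.1 and 9.9 as a separate point. The clinical rescue criteria are not in question here.

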9.5.1 Hierarchical testing procedure

For the confirmatory analyses, the following a priori defined hierarchical inferential test order will be applied for the control of the type 1 error rate across the planned multiple comparisons. The primary endpoint and key secondary endpoints will be inferentially evaluated within the FAS in the following order, where inference will proceed at the two-sided 0.05 criterion significance level until the first failure to reject the null hypothesis for a dasiglucagon versus placebo comparison:

- Primary: Time to plasma glucose recovery
- Key secondaries 1-4: Plasma glucose recovery within 30 minutes, within 20 minutes, within 15 minutes, and within 10 minutes after study drug injection without administration of rescue IV glucose.
- Key secondaries 5-8: Plasma glucose changes from baseline (CFB) within 30 minutes, within 20 minutes, within 15 minutes, and within 10 minutes after study drug injection or at the time of rescue.

The GlucaGen versus placebo comparisons will not be included in the inferential testing hierarchy, since the efficacy of GlucaGen is previously established, and these comparisons are intended to support the validity of the study for the dasiglucagon versus placebo comparisons.

Analogous supportive sensitivity analyses will be conducted in the PP set, but without inference intent.

9.5.2 Primary confirmatory endpoint

Time to plasma glucose recovery. Plasma glucose recovery is defined as first increase in plasma glucose of ≥ 20 mg/dL (1.1 mmol/L) from baseline during the hypoglycemic clamp procedure without administration of rescue IV glucose.

9.5.2.1 Primary analysis

The primary endpoint will be summarized using Kaplan-Meier (KM) estimates stratified by treatment group and injection site. The treatment group difference between dasiglucagon and placebo will be evaluated inferentially using a pairwise two-sided log-rank test.

In the primary analysis, recovery cannot be achieved in those subjects where IV glucose treatment is administered. Those subjects who receive IV glucose will be censored (i.e. set to ‘not recovered’) at 45 minutes after dosing.

In sensitivity analyses, the time to plasma glucose recovery will be analyzed 1) without censoring for those subjects who require rescue IV glucose before 45 minutes and 2) with censoring at the time of administration of rescue IV glucose before 45 minutes.

The primary endpoint will additionally be analyzed using a Cox proportional hazards (CPH) time to event statistical model, if the hazards by treatment group can be assumed proportional using a graphical comparison of log-minus-log survival curves and no more than two-thirds of the recovery times are censored in each treatment group. The CPH model will be used for inferences, with treatment group and injection site modeled as categorical effects, and baseline plasma glucose modeled as a continuous covariate. The treatment group rate ratios, active versus placebo, will be estimated together with the 95% confidence intervals, and pairwise treatment group inferences (dasiglucagon vs placebo, GlucaGen vs placebo) will be evaluated using two-sided likelihood ratio tests.

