6.2 Treatment assignment and randomization

Subjects successfully completing screening and who fulfill entry eligibility and randomization criteria will be randomized to one of three treatment groups in a ratio of 2:1:1:

- Test treatment: Dasiglucagon, liquid formulation, 1 mg/mL, 0.6 mL delivered in a prefilled syringe.
- Placebo treatment: Placebo, liquid formulation, 0.6 mL delivered in a prefilled syringe.
- Reference treatment: Recombinant glucagon hydrochloride, 1 mg for reconstitution.

Randomization will be performed using a fixed-block randomization scheme. The randomization scheme will be generated prior to the initiation of the study by an independent statistician/programmer who will not be a member of the study team; all investigators will not be aware of the block size of the randomization scheme.

Randomization will be stratified by treatment group and by injection site (abdomen, buttocks, or thigh) and controlled via the IWRS.

Subjects will be randomized to study treatment using an interactive, automated system which has been validated for the intended use under the International Society of Pharmaceutical Engineers Good Automated Manufacturing Process guidelines, 21CFR Part 11 (FDA regulation for Electronic Records and Electronic Signatures) and the International Conference on Harmonization (ICH) Guidance E6 for Industry on Good Clinical Practice (GCP).

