9.5.3.1 Confirmatory analysis

The key secondary incidence variables (plasma glucose recovery within 30 minutes, within 20 minutes, within 15 minutes, within 10 minutes, in hierarchical order for inference) will be analyzed using descriptive statistics (frequency and percentage) by treatment group. Inferential treatment group comparisons will be assessed via pairwise tests of independent binomial proportions (dasiglucagon versus placebo, GlucaGen versus placebo) using Fisher’s exact test for each pairwise comparison.

The key secondary endpoints of plasma glucose CFB within 30 minutes, within 20 minutes, within 15 minutes, and within 10 minutes after study drug injection or at the time of rescue, will be analyzed with the plasma glucose CFB at rescue carried forward in those subjects who require rescue IV glucose before plasma glucose ≥ 20 mg/dL recovery. Each of these CFB variables will be analyzed using an Analysis of Covariance model, with treatment group modeled as a fixed effect and with the baseline plasma glucose modeled as a covariate. The dasiglucagon versus placebo treatment group difference will be evaluated inferentially as a least squares means contrast, using a two-sided t-test at the

0.05 significance level, first for the 30 minute CFB, and then sequentially for the 20 minute, 15 minute, and 10 minute variables, until the first failure to reject.

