9.7.4 Other safety data

Incidence of rescue infusion of IV glucose during the hypoglycemic clamp procedure will be analyzed using descriptive statistics (frequency and percentage) by treatment group. Inferential treatment group comparisons will be assessed via pairwise tests of independent binomial proportions (dasiglucagon versus placebo, GlucaGen versus placebo).

Time to first rescue infusion of IV glucose during the hypoglycemic clamp procedure will be evaluated using a KM time to event statistical model, with treatment group and injection site as stratification factors. Differences between the KM curves (dasiglucagon versus placebo, GlucaGen versus placebo) will be evaluated inferentially using pairwise two-sided stratified log-rank tests. If the endpoint is never met, the time of the last plasma glucose measurement will be the censoring time.

Vital signs, physical examination, 12-lead ECG and local tolerability data will be summarized using descriptive statistics.

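### The primary log-rank test and the glucose ANCOVAs omit injection site, the randomisation stratum; including it is a cheap gain in efficiency if site materially affects speed of response

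*Protocol*

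**What the plan says.** Section 6.2 makes injection site a design factor: "Randomization will be stratified by treatment group and by injection site (abdomen, buttocks, or thigh) and controlled via the IWRS". Section 8.2.3.1 has the dose given at the site that this stratification assigns.

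The analyses then treat site in two ways.

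*Site included.* The descriptive summary in 9.5.2.1 uses it: "The primary endpoint will be summarized using Kaplan-Meier (KM) estimates stratified by treatment group and injection site". So does the additional Cox model in the same section, "with treatment group and injection site modeled as categorical effects, and baseline plasma glucose modeled as a continuous covariate". For time to first rescue infusion, section 9.7.4 names treatment group and injection site as stratification factors, and the curves "will be evaluated inferentially using pairwise two-sided stratified log-rank tests".

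*Site not included.* The test that decides the trial is given in 9.5.2.1 and the synopsis as follows: "The treatment group difference between dasiglucagon and placebo will be evaluated inferentially using a pairwise two-sided log-rank test". The change-from-baseline analysis in 9.5.3.1 is an "Analysis of Covariance model, with treatment group modeled as a fixed effect and with the baseline plasma glucose modeled as a covariate". Section 9.5.4.1 describes the analysis of time to ≥70 mg/dL as analogous to the primary one, names only treatment group as a factor and uses plain log-rank tests. Its AUC model has treatment and baseline glucose only.

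**The concern.** When randomisation is stratified on a factor that predicts outcome, the arms are balanced on it by design. An analysis that ignores the factor still counts the between-site spread as noise in the treatment comparison. For a log-rank test, pooling sites with different recovery rates also pulls the overall rate ratio towards one. Both effects cost power.

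The protocol gives a safety endpoint the test that matches the design and withholds it from the primary endpoint. The primary test is also the gate. Under 9.5.1, a failure there stops inference on all eight key secondaries.

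**Working it through.** **Inputs.** Section 9.1 gives exponential recovery times with medians of 10 minutes (dasiglucagon) and at least 20 minutes (placebo), 78 versus 39 subjects, 45 minutes of follow-up, two-sided 5% and 90% power. Section 7.1.1 gives glucose samples at 4, 6, 8, 10, 12, 15, 17, 20, 25, 30 and 40 minutes within that window. The documents give neither a site effect nor stratum sizes. Assumed here: three equal strata (26 and 13 subjects per site) and a range of recovery-rate multipliers across the sites.

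**1. The plan's own figure.** Expected recoveries are 78 × (1 − 2^(−45/10)) + 39 × (1 − 2^(−45/20)) = 74.6 + 30.8 = 105.4. The Schoenfeld formula gives power = Φ(√(105.4 × 2/3 × 1/3) × ln 2 − 1.96) = Φ(3.354 − 1.96) = Φ(1.394) = 0.918. Simulating the plain log-rank test with no site effect gives 0.904. The stated 90% is reproduced.

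**2. Site effect at the 20-minute placebo floor.** Simulated power, 3,000 runs, planned sampling times, multipliers in both arms:

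| Assumed multipliers | Fastest ÷ slowest | Unstratified | Stratified | Loss from not stratifying |
|---|---|---|---|---|
| none | 1 | 90.0% | 89.6% | −0.4 |
| 1.3 / 1 / 0.75 | 1.7 | 86.4% | 87.4% | 1.0 |
| 1.6 / 1 / 0.6 | 2.7 | 84.8% | 88.9% | 4.1 |
| 2 / 1 / 0.5 | 4 | 76.5% | 87.2% | 10.7 |

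The simulation standard error near 87% is √(0.87 × 0.13 / 3000) = 0.6 point. A separate run gave 90.0/88.9, 86.1/87.0, 84.0/88.5 and 75.3/86.9, the same pattern. If site acts only in the active arm, which is plausible for an absorption effect, multipliers of 2/1/0.5 give 76.5% versus 88.7% (4,000 runs).

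**3. Type I error.** With both medians at 20 minutes and multipliers 2/1/0.5 in both arms, the rejection rate is 2.9% unstratified and about 5.2% stratified (4,000 runs, standard error √(0.05 × 0.95 / 4000) = 0.3 point). The unstratified test is conservative; the stratified one is close to nominal.

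**4. Longer placebo medians.** Section 9.1 expects more than 20 minutes. Power, unstratified versus stratified (2,000 runs, both arms):

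| Multipliers | Placebo median 25 min | Placebo median 30 min |
|---|---|---|
| 1.3 / 1 / 0.75 | 98.0% vs 98.2% | 99.7% vs 99.8% |
| 1.6 / 1 / 0.6 | 96.7% vs 98.1% | 99.8% vs 99.9% |
| 2 / 1 / 0.5 | 94.9% vs 98.3% | 98.8% vs 99.6% |

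The largest losses are 98.3 − 94.9 = 3.4 points at 25 minutes and 99.6 − 98.8 = 0.8 point at 30 minutes. At 40 minutes both tests are at 100% for these multipliers.

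**5. ANCOVA.** If site explains a share R² of the residual variance, a comparison with 90% power without site has power Φ((1.96 + 1.2816)/√(1 − R²) − 1.96) with it. That is 90.6% for R² = 2%, 91.4% for 5% and 92.7% for 10%.

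**The case against.** **A stratified test may have been meant.** The sentence just before the primary test stratifies the Kaplan-Meier estimates by site, and section 9 lets the SAP, not shown here, refine details. The intention is possible, but the text does not carry it. Section 9.7.4 says stratified where it means it, and 9.5.4.1, analogous to the primary analysis, names treatment group alone. The ANCOVA terms are listed outright and leave no such room.

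**The power loss is shown at the plan's worst case.** This largely stands. Sample size was set by the safety database, 20 minutes is a floor, and step 4 shows little loss above it. A reader might infer that the primary analysis is underpowered; the documents do not support that.

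**Every site effect is assumed.** This also stands. The protocol reports no difference between abdomen, buttocks and thigh. A reader might infer that any site effect costs power, but at the mildest multipliers the difference is about 1 point, near simulation error.

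**Validity is not at stake.** Agreed. A reader might infer that ignoring the stratum inflates false positives. Step 3 shows the opposite, so a positive primary result would remain credible.

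**The Cox model already adjusts for site.** It does, but it is an additional analysis. It is run only if hazards look proportional and no more than two-thirds of times are censored in each group, so it does not replace the confirmatory test.

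**The Fisher tests for key secondaries 1–4 also ignore site.** True. Stratifying them would mean replacing the test rather than adding a phrase, so the fix below leaves them alone.

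**Conclusion.** The point holds as one of efficiency and consistency. The primary log-rank test, the ≥70 mg/dL log-rank test and the change-from-baseline and AUC ANCOVAs omit the randomisation stratum, while the Cox model and the time-to-rescue test account for it.

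If site materially affects speed of recovery, the unstratified primary test is conservative. At the 20-minute floor it gives up about 1, 4 or 11 points of power for fastest-to-slowest ratios of 1.7, 2.7 or 4. The loss is at most about 3 points at a 25-minute placebo median and 1 point or less from 30 minutes. The ANCOVA gain is about 0.6 to 2.7 points if site explains 2% to 10% of residual variance.

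These sizes rest on assumed site effects, equal strata and exponential times. Severity is modest: it is the sponsor's chance of success that is at risk, not the validity of a positive finding.

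**What to change.** - In 9.5.2.1 and the synopsis, specify the primary test as a two-sided log-rank test stratified by injection site (abdomen, buttocks, thigh).
- In 9.5.4.1, do the same for time to ≥70 mg/dL.
- In 9.5.3.1, 9.5.4.1 and the synopsis, add injection site as a fixed effect to the change-from-baseline and AUC ANCOVA models. The PK models for AUC and C_max follow by the cross-reference in 9.5.5.1.
- If the SAP already stratifies these analyses, align the protocol wording with it.

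The cost is a phrase per analysis. If site has no effect, stratifying gives up about 0.5 to 1 point of power in the primary test (90.0% to 89.6% in one simulation, 90.0% to 88.9% in the other). In the ANCOVAs it uses two degrees of freedom (three sites minus one). The change should be made before unmasking.
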